5.3.1 Localization, Simulation, and Immobilization

Simulation and treatment position will be determined by the treating radiation oncologist and team. Patients should be optimally positioned for stereotactic body radiation therapy with alpha cradles, aquaplast masks, or other methods of immobilization. The use of devices to alter dose distributions, such as bolus or lead shields, are allowed. Use of techniques to control and/or accommodate tumor motion may also be employed in constructing the planning target volume (PTV).

A treatment planning CT scan or MRI in the treatment position will be required to define the PTV. The extent of the CT scan will be determined at the discretion of the treating physician. A CT scan slice thickness of ≤ 5 mm should be employed.

5.3.2 Treatment Planning/Target Volumes

The definitions for the GTV, PTV and normal structures used in this protocol generally conform to the 1993 ICRU report #50 titled Prescribing, Recording and Reporting Photon Beam Therapy.

[figure not shown]
5.3.2.1 Target Volumes and Normal Structures

Target Volumes

Gross Tumor Volume (GTV): Contour using all available clinical and radiographic information. Fusion of other diagnostic imaging to delineate the GTV is allowed. Construction of an iGTV using 4DCT imaging is allowed. For boney lesions of the spine, the entire involved vertebral body may be included in the GTV.

Planning Target Volume 2000 cGy (PTV_2000): Represents a geometric expansion of the GTV (or iGTV) of up to 1.0 cm. The PTV should be reduced as not to extend beyond the patient (i.e. in to air) and may be reduced as to not extend into skin (i.e. external contour contracted by 3-5 mm).

Planning Target Volume 6670 cGy (PTV_6670): Spheres with diameter 1.5 cm should be placed 6 cm apart as measured from center to center inside the GTV. The spheres should be placed to maximize the number of whole spheres within the GTV. There should be 3 cm between axial slices in which spheres are placed. Vertices will be offset such as to create an octahedron between 3 slices on which spheres are placed. See the figure below for a geometric explanation. Crop all sphere volume extending outside of the GTV.

Geometric representation of sphere placement. Yellow dots represent the center of each sphere. Short dashes represent in-plane distances, dotted lines represent out-of-plane distances. Note that superior/inferior axial planes have spheres offset by 3 cm in-plane. To the right are axial slices representing yellow sphere placement in each plane. A blue diamond is represented to indicate vertices in the reference axial plane, and the center of vertices in planes 3 cm superior and inferior to this.

Normal structures: Relevant normal structures and their dose constraints are described in the table below. Each normal structure should be contoured in its entirety.

5.3.2.2 Radiation Treatment Planning

CT-based planning with tissue inhomogeneity correction is required. Daily IGRT is required. Motion management strategies such as breath holding, respiratory gating, fluoroscopy, and MR-guided daily adaptive therapy are allowed.

5.3.2.3 Planning Objectives and Normal Tissue Constraints

The normal tissues in the table below are to be contoured in their entirety when present on the CT simulation scan.

The following organs and doses are guidelines for the radiation treatment plan. **Organ at risk tolerance levels cannot be exceeded.** Under coverage of PTV targets in order to meet OAR constraints is allowed.

- PTV_2000: at least 95% should be covered by 20 Gy. Keeping D_{max} within the PTV_2000 and outside the PTV_6670 to less than 24 Gy is recommended but not required.
- PTV_6670: at least 95% should be covered by 66.7 Gy. A D_{min} of at least 60 Gy within vPTV is recommended.

| Serial Tissue | Max point* dose (Gy) |
|-------------------------------|----------------------|
| Optic pathway | 25 |
| Cochlea | 22 |
| Brainstem (excluding medulla) | 31 |
| Spinal cord and medulla | 28 |
| Cauda equina | 31.5 |
| Sacral plexus | 32 |
| Esophagus | 35 |
| Brachial plexus | 32.5 |
| Heart/pericardium | 38 |
| Great vessels | 53 |
| Trachea and large bronchus | 40 |
| Bronchi | 33 |
| Skin | 38.5 |
| Stomach | 35 |
| Bile duct | 41 |
| Duodenum | 26 |
| Jejunum/ileum | 32 |
| Colon | 40 |
| Rectum | 55 |
| Ureter | 45 |
| Bladder wall | 38 |

*A point is defined as volume ≤ 0.035 cc)

| Parallel Tissue | Critical Dose (Gy) | Critical Volume |
|-----------------|--------------------|--------------------|
| Lungs - GTV | 12.5 | < 1500 cc |
| | 13.5 | < 1000 cc < 37% |
| Liver | 21 | < 700 cc |

| | | |
|---|----|----------|
| Renal cortex (bilateral) | 28 | < 200 cc |
| Femoral Heads (Right & Left) | 30 | <10 cc |

5.3.3 Dose Specifications

For Lattice SBRT, the daily prescription dose will be 20 Gy to be delivered to the PTV_2000 with a SIB of 66.7 Gy to be delivered to the PTV_6670 over 5 fractions (4 Gy and 13.34 Gy to the PTV_2000 and PTV_6670 per day, respectively). All doses will be prescribed to the periphery of the PTVs. In general, the prescription isodose line (generally 93-98%) chosen should encompass at least 95% of the PTV. Under coverage of the PTV to meet dose constraints is allowed.

The maximum point dose, minimum point dose, and the mean dose to the PTV will also be reported.

5.3.4 Technical Factors

The guidelines for VMAT in this trial will conform to the policies set by the Advanced Technology Consortium (ATC) and the National Cancer Institute (NCI). Each of the target volumes and normal structures listed below must be delineated on each slice from the 3D planning CT in which that structure exists.

5.3.5 Radiation Quality Assurance

Radiation quality assurance will be evaluated by a Medical Physics team. Prior to treatment, plan quality will be assessed with an ion chamber and film-based dosimeters.

5.4 Patient-Reported Quality of Life Outcome and Toxicity Measures

Symptom response and patient-reported quality of life will be measured using the pain numeric rating scale, PRO-CTCAE (abridged as indicated in Appendix D), PROMIS Global, Physical Function, Pain Interference, Anxiety, and Depression questionnaire at the following time points:

1. Within 2 weeks prior to the start of radiotherapy
2. Within 2 weeks after completion of radiotherapy
3. At 30 days after radiotherapy
4. At 90 days after radiotherapy

The patient reported outcomes measures will be conducted using a computer-assisted interview program and may be done in person before/after a routine office visit or over the phone at the preference of the study participant. Patient reported outcomes may also be collected online.

5.5 Acquisition of Blood for Research

Refer to Section 8.0.

5.6 Definitions of Evaluability

All patients enrolled on the study are evaluable for toxicity if they have received at least one fraction of radiation. Patients are evaluated from first receiving study treatment until 90 days after the conclusion of treatment or death.

5.7 Concomitant Therapy and Supportive Care Guidelines

Patients may not receive any concurrent cytotoxic chemotherapy or VEGF inhibitors with radiation. The interval from last receipt of cytotoxic chemotherapy or VEGF inhibitors to the initiation (or re-initiation) of subsequent therapy will be at physician discretion. Supportive care will be consistent with standards for palliative radiotherapy, directed by the treating physician.

5.8 Women of Childbearing Potential

Women of childbearing potential (defined as women with regular menses, women with amenorrhea, women with irregular cycles, women using a contraceptive method that precludes withdrawal bleeding, and women who have had a tubal ligation) are required to have a negative serum/urine pregnancy test within 20 days prior to the first dose of radiation.

Female and male patients (along with their female partners) are required to use two forms of acceptable contraception, including one barrier method, during participation in the study and for 6 months following the last dose of radiation.

If a patient is suspected to be pregnant, radiation should be immediately discontinued. In addition a positive urine test must be confirmed by a serum pregnancy test. If it is confirmed that the patient is not pregnant, the patient may resume therapy.

If a female patient or female partner of a male patient becomes pregnant during therapy or within 6 months after the last dose of radiation, the investigator must be notified in order to facilitate outcome follow-up.

5.9 Duration of Therapy

If at any time the constraints of this protocol are considered to be detrimental to the patient's health and/or the patient no longer wishes to continue protocol therapy, the protocol therapy should be discontinued and the reason(s) for discontinuation documented in the case report forms.

In the absence of treatment delays due to adverse events, treatment may continue for a maximum of 2 weeks or until one of the following criteria applies:

- Documented and confirmed disease progression
- Death
- Adverse event(s) that, in the judgment of the investigator, may cause severe or permanent harm or which rule out continuation of study drug
- General or specific changes in the patient's condition render the patient unable to receive further treatment in the judgment of the investigator
- Suspected pregnancy
- Serious non-compliance with the study protocol
- Lost to follow-up
- Patient withdraws consent
- Investigator removes the patient from study
- The Siteman Cancer Center decides to close the study

Patients who prematurely discontinue treatment for any reason will still be followed as indicated in the study calendar.

5.10 Follow-up Specifications

5.10.1 Duration of Follow Up

Patients will be followed at 14, 30, and 90 days after completion of radiotherapy. Patients removed from study for unacceptable adverse events will be followed until resolution or stabilization of the adverse event. Patients may be followed in-person during visits, medical records review, phone calls, office visits, and assessment of any other clinically relevant materials after completion of therapy.

5.11 Lost to Follow-Up

A participant will be considered lost to follow-up if he or she fails to return for 4 weeks and is unable to be contacted by the study team.

The following actions must be taken if the participant fails to return to clinic for a required study visit:

- The study team will attempt to contact the participant and reschedule the missed visit within 1-2 weeks and counsel the participant on the importance of maintaining the assigned visit schedule and ascertain if the participant wishes to and/or should continue in the study.
- Before a participant is deemed lost to follow-up, the investigator or designee will make every effort to regain contact with the participant (where possible, 3 telephone calls and, if necessary, a certified letter to the participant's last known mailing address). These contact attempts should be documented in the participant's medical record or study file.
- Should the participant continue to be unreachable, he or she will be considered to have withdrawn from the study with a primary reason of lost to follow-up.

6.0 RADIATION THERAPY DOSE/DELAYS MODIFICATIONS

The planned course of radiation therapy is five fractions delivered every other day to each lesion. For plans unable to meet dose constraints to OARs, under coverage of the PTV in order to meet the constraints is recommended. Patients with delayed treatment starts of any duration may be treated using existing or new plans at physician discretion. Continuance of treatment for delays while on-treatment will be at the discretion of the treating physician.

7.0 REGULATORY AND REPORTING REQUIREMENTS

The entities providing oversight of safety and compliance with the protocol require reporting as outlined below. Please refer to Appendix B for definitions and Appendix C for a grid of reporting timelines.

Adverse events will be tracked from start of treatment through 90 days following the completion of radiotherapy. All adverse events must be recorded on the toxicity tracking case report form (CRF) with the exception of:

- Baseline adverse events, which shall be recorded on the medical history CRF
- AEs that do not fall under the following categories
 - Gastrointestinal
 - Hepatobiliary
 - Immune system
 - Metabolic
 - Nervous system
 - Renal and urinary
 - Respiratory
 - Skin disorders
- AEs that are grade 1

Refer to the data submission schedule in Section 9.0 for instructions on the collection of AEs in the EDC.

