9.1 Adverse Event Collection in the Case Report Forms

All adverse events that occur beginning with start of treatment (minus exceptions defined in Section 7.0) must be captured in the Toxicity Form. Baseline AEs should be captured on the Medical History Form.

Participant death due to disease progression should be reported on the Toxicity Form as grade 5 disease progression. If death is due to an AE (e.g. cardiac disorders: cardiac arrest), report as a grade 5 event under that AE. Participant death must also be recorded on the Death Form.

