10.0 DATA AND SAFETY MONITORING

In compliance with the Washington University Institutional Data and Safety Monitoring Plan, the Principal Investigator will provide a Data and Safety Monitoring (DSM) report to the Washington University Quality Assurance and Safety Monitoring Committee (QASMC) semi-annually beginning six months after accrual has opened (if at least one patient has been enrolled) or one year after accrual has opened (if no patients have been enrolled at the six-month mark).

The Principal Investigator will review all patient data at least every six months, and provide a semi-annual report to the QASMC. This report will include:

- HRPO protocol number, protocol title, Principal Investigator name, data coordinator name, regulatory coordinator name, and statistician
- Date of initial HRPO approval, date of most recent consent HRPO approval/revision, date of HRPO expiration, date of most recent QA audit, study status, and phase of study
- History of study including summary of substantive amendments; summary of accrual suspensions including start/stop dates and reason; and summary of protocol exceptions, error, or breach of confidentiality including start/stop dates and reason
- Study-wide target accrual
- Protocol activation date
- Average rate of accrual observed in year 1, year 2, and subsequent years
- Expected accrual end date
- Objectives of protocol with supporting data and list the number of participants who have met each objective
- Measures of efficacy (phase I studies only if efficacy is objective of the protocol)
- Measures of efficacy
- Early stopping rules with supporting data and list the number of participants who have met the early stopping rules
- Summary of toxicities
- Abstract submissions/publications
- Summary of any recent literature that may affect the safety or ethics of the study

The study principal investigator and Research Patient Coordinator will monitor for serious toxicities on an ongoing basis. Once the principal investigator or Research Patient Coordinator becomes aware of an adverse event, the AE will be reported to the HRPO and QASMC according to institutional guidelines.

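### The adverse-event recording rule in Section 7.0 leaves out organ classes that the primary safety endpoint and the stopping rule include, with no exception for grade 3 or higher

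*Combined protocol and SAP*

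**What the plan says.** **What is to be counted.** Section 2.0 defines the primary endpoint as the rate of treatment-related, non-hematologic CTCAE v5.0 toxicity of grade 3 or higher. Section 11.2 expresses it as a percentage of patients. Section 11.6 applies a stopping boundary to non-hematological events of grade 3 or higher. None of the three restricts the organ class.

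**What is to be recorded.** Section 7.0 opens broadly: "Adverse events will be tracked from start of treatment through 90 days following the completion of radiotherapy". It then sends all adverse events to the toxicity form with three exceptions: baseline events, grade 1 events, and "AEs that do not fall under the following categories". The categories are gastrointestinal, hepatobiliary, immune, metabolic, nervous system, renal and urinary, respiratory, and skin. Section 9.1 carries the exceptions over: "All adverse events that occur beginning with start of treatment (minus exceptions defined in Section 7.0) must be captured in the Toxicity Form".

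**What is restored.** Section 9.1 brings back fatal events only: "If death is due to an AE (e.g. cardiac disorders: cardiac arrest), report as a grade 5 event under that AE". It also puts another kind of death on the same form: "Participant death due to disease progression should be reported on the Toxicity Form as grade 5 disease progression".

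**Other safety channels.** Section 7.2 requires events that need no expedited reporting to be captured in the EDC. Under Section 10.0 the investigator and coordinator "will monitor for serious toxicities on an ongoing basis". The semi-annual report must include "Objectives of protocol with supporting data and list the number of participants who have met each objective", "Early stopping rules with supporting data and list the number of participants who have met the early stopping rules", and a summary of toxicities.

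**The concern.** The collection rule is narrower than the quantity it has to feed. The grade 1 exemption is a separate bullet, so the organ-class exemption applies at every grade, and site staff who follow 7.0 and 9.1 to the letter need not enter a non-fatal grade 3 or 4 event from an unlisted class.

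Such events are foreseeable on the protocol's own terms. Section 9.1 uses cardiac disorders as its example heading, that heading is not one of the eight, and Section 5.3.2.3 sets a dose limit for heart and pericardium. Great vessels, cochlea and femoral heads are also dose-limited there and appear to fall outside the list, but the documents do not give the class mapping, so the point rests on cardiac events.

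Safety is the only primary objective. An omission caused by this exemption acts in one direction: it lowers both the reported toxicity rate and the count compared with the stopping boundary.

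**Working it through.** **1. Compare the rules for a non-fatal grade 3 cardiac event judged related to treatment.**

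| Question | Section | Answer |
|---|---|---|
| Part of the primary endpoint? | 2.0, 11.2 | Yes |
| Part of the stopping count? | 11.6 | Yes |
| Required on the Toxicity Form? | 7.0, 9.1 | No: class not listed, no grade condition |
| Restored by the death rule? | 9.1 | No: not fatal |
| Source of the two counts named? | 11.2, 11.6, 9.0, 10.0 | No |

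**2. One uncounted patient.** This means a patient whose only qualifying event is in an unlisted class and is not counted. The documents give two sample sizes: 10 (Synopsis, 4.5) and 20 (11.1, 11.4). The rate falls by 1/10 = 10 points or 1/20 = 5 points. Around the expected 30%, with exact (Clopper-Pearson) 95% limits:

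| Counted | Rate | 95% limits |
|---|---|---|
| 3/10 | 30% | 6.7% to 65.2% |
| 2/10 | 20% | 2.5% to 55.6% |
| 6/20 | 30% | 11.9% to 54.3% |
| 5/20 | 25% | 8.7% to 49.1% |

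At the first entry of the boundary table, 4 events in 4 patients halt accrual. With one of the four uncounted the count is 3, below the boundary of 4.

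**3. Reproduce the plan's stopping probabilities.** The boundary row as it appears in 11.6 has 11 values for 12 columns. A search over boundaries starting at 4 and rising by 0 or 1 per patient found one that fits: 4, 5, 5, 6, 6, 6, 7, 7, 8, 8, 9, 9 for n = 4 to 15, with a maximum of 15 patients. An exact binomial recursion with it gives 0.0447, 0.1707, 0.4101, 0.6957, 0.9052, 0.9878 and 0.9998 at true rates of 0.3 to 0.9. These match the early-stopping column in 11.6.

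**4. Illustration of under-counting.** Let f be the share of affected patients whose only qualifying event is in an unlisted class and is not counted. The documents give no value, so f is an assumption. The observed rate is p(1 − f). At p = 0.40, the rate that 11.6 calls not desired:

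| f | Observed rate | Stopping probability |
|---|---|---|
| 0 | 0.400 | 17.1% |
| 1% | 0.396 | 16.3% |
| 5% | 0.380 | 13.6% |
| 10% | 0.360 | 10.7% |

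**5. Why naming the Toxicity Form needs an exclusion.** Section 9.1 enters progression deaths on that form as grade 5. Suppose they were counted and a share q of patients died of progression in the window, independently of toxicity (q is also an assumption). The observed rate is 1 − (1 − p)(1 − q). At the acceptable p = 0.30:

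| q | Observed rate | Stopping probability |
|---|---|---|
| 0 | 0.300 | 4.5% |
| 5% | 0.335 | 7.6% |
| 10% | 0.370 | 12.1% |
| 20% | 0.440 | 25.4% |

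**The case against.** The strongest reply is that losing such an event would take several failures at once. Section 7.0 tracks events for 90 days, the Schedule of Activities has repeated adverse-event reviews, 5.1 plans toxicity evaluation at 14, 30 and 90 days, and 11.6 calls for continuous review, all without a class limit. Section 9.0 lists a Follow Up Form whose content is not given, 7.2 asks for EDC capture, and Appendix C sends adverse events to the toxicity table of the monitoring report. Section 5.3.2.3 says organ tolerances may not be exceeded, which should make such events less likely. The endpoint is defined without reference to any form, so an analyst following 11.2 should count every qualifying event. It is also per patient, so someone with a qualifying event in a listed class is counted anyway.

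Much of this stands. It limits the claim to a possible miss and leaves its frequency unknown. It does not close the gap: none of these channels names the source of the endpoint or stopping counts, and none requires a non-fatal grade 3-4 event in an unlisted class to be on the Toxicity Form. Section 7.2 names no form or grade and, read broadly, conflicts with 7.0. The monitoring in 10.0 concerns serious toxicities, and Appendix B defines seriousness by outcome, so a grade 3 event need not qualify. An analyst can count only what was recorded.

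It is also fair to say that progression deaths work in the opposite direction, and that a treatment-related endpoint should already leave them out. They matter here because the remedy draws the counts from the form that holds them, and 11.6 leaves unclear whether attribution applies.

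**Conclusion.** The concern holds and should be fixed. The recording rule in 7.0 and 9.1 is narrower than the primary endpoint and the stopping rule, and cardiac events show this from the documents' own wording. Following the rule as written can bias the only primary endpoint and the stopping count downward.

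The firm figures are those for one uncounted patient: 10 points at 10 patients, 5 points at 20, and a halt avoided at four patients. The stopping probabilities are illustrations. They rest on assumed values of f and q, on a boundary inferred by matching the plan's table, and on a maximum of 15 patients. Confidence is high that the rules conflict; the documents cannot show that an event would be lost.

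**What to change.** 1. **Section 7.0, and through it 9.1.** Limit the organ-class exemption to events below grade 3. Suggested text: *Every non-hematologic adverse event of grade 3 or higher, in any organ class, is entered on the Toxicity Form with its attribution.*
2. **Sections 11.2 and 11.6.** Name the source and the exclusion. Suggested text: *The primary endpoint and the stopping count are taken from non-hematologic events of grade 3 or higher on the Toxicity Form, applying the recorded attribution as this section's event definition requires. Disease-progression deaths entered as grade 5 under Section 9.1 are not counted.*
3. **Section 11.6.** The event is described in one place as treatment-emergent and in another as related to Lattice SBRT. Reconcile the two so that it is clear whether attribution filters the stopping count; the text in item 2 cannot be applied in 11.6 until this is done.

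The cost is one sentence in 7.0, two in 11.2 and 11.6, the wording reconciliation, and a few more form entries, with attribution recorded for each grade 3 or higher event, in 10 to 20 patients followed for 90 days.
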